11.2 Lenalidomide

Likely Side Effects: those occurring in more than 20% or more than 20 out of 100 persons who receive lenalidomide:

- Low number of white blood cells (with or without fever)
- Anemia (lowered red blood cells)
- Decrease in cells that help your blood clot (lowered platelets)
- Swelling in legs and/or extremities
- Diarrhea
- Constipation
- Nausea
- Feeling weak and unwell, fatigue
- Fever
- Chills
- Rash
- Pain including muscles, joints, back, and non-cardiac chest pain
- Dizziness
- Shaking or tremor
- Shortness of breath
- Upper respiratory tract infection

Less Likely Side Effects: those occurring in 5-20% or 5 to 20 out of 100 persons who receive lenalidomide:

- Vision Blurred
- Altered sense of taste
- Pain or decreased sensation of touch
- Pneumonia
- Urinary tract infection
- Increased sweating
- Dry skin
- Itching
- Decreased appetite
- Weight loss
- Vomiting
- Abdominal pain
- Dry mouth
- Electrolyte imbalance in blood
- Blood clot in lower or upper extremities
- Lowered level of consciousness with drowsiness, listlessness, and apathy

- Abnormal liver lab tests
- Loss of fluid
- Muscle weakness
- Tingling of skin
- High or low blood pressure

Rare and/or Potentially Serious Side Effects: these have occurred in less than 5% or in less than 5 out of 100 persons who receive lenalidomide:

- Lowered white blood cells with fever
- Blood clot to lung
- Irregular heart beat
- Congestive heart failure – abnormal functioning of heart leading to fluid in lungs and extremities
- Stroke
- Immune destruction of red blood cells (autoimmune hemolytic anemia)
- Slow heart rate or fast heart rate
- Heart attack
- Blindness
- Mood swings, hallucinations
- Gastrointestinal bleed
- Severe skin allergic reactions: lining of the nose, mouth, stomach and intestines or rash leading to the separation of the top layer of skin, swelling under the skin
- Rapid death of cancer cells where the accumulating contents of dying cancer cells cause an imbalance in the chemistry of the body which can lead to kidney damage.
- Lenalidomide, a thalidomide analogue, caused limb abnormalities in a developmental monkey study similar to birth defects caused by thalidomide in humans. If lenalidomide is used during pregnancy, it may cause birth defects or death to a developing baby.
- Second primary cancers

11.3 Dexamethasone

Likely Side Effects: those occurring in more than 20% or more than 20 out of 100 persons who receive lenalidomide:

- Increase in appetite
- Weight gain
- Fatigue
- Fluid retention, which can lead to swelling in the legs, arms and within the face
- High blood pressure
- Rise in the blood sugar
- Problems with low levels of potassium in the blood
- Menstrual cycle disturbances
- Depression or Mood swings or changes in personality
- Trouble with sleeping
- Dizziness
- Headache
- Slow wound healing
- Thin, fragile skin, black and blue marks
- Increased sweating and/or flushing
- Increase in body hair
- Bone thinning, which can lead to spinal fracture or destruction or fracture of the long bones (thigh/hip and upper arm/shoulder)
- Hormonal disturbances during times of stress or illness
- Hiccups
- Nausea
- Rash – mild acne
- Increased risk of infections. This can be a serious, potentially life threatening event.
- Yeast infections

Less Likely Side Effects: those occurring in 5-20% or 5 to 20 out of 100 persons who receive lenalidomide:

- Stomach ulcers or worsening or irritation or existing ulcers. This can be serious, potentially life threatening event.
- Muscle weakness or loss of muscle mass
- Inflammation of the pancreas
- Cataract formation
- Glaucoma
- Rupture of tendons
- Vein blood clots in the veins of the legs or lungs. This can be a serious potentially life threatening event.

Rare and/or Potentially Serious Side Effects: these have occurred in less than 5% or in less than 5 out of 100 persons who receive lenalidomide:

- Severe allergic reactions (including facial redness, shortness of breath, profuse perspiration, abdominal cramps, fast heart beat, and low blood pressure - severe allergic reactions).
- Brain swelling.
- Convulsions.
- Formation of a hole in the small and/or large bowel particularly in people with preexisting bowel problems. This can be a serious, potentially life threatening event.
- Irritation and bleeding of the esophagus (the tube from the mouth to the stomach)
- If you are more prone to heart disease, you may experience heart failure
- Aseptic necrosis (bone death) of the hip

12.0 CRITERIA FOR THERAPEUTIC RESPONSE/OUTCOME ASSESSMENT

Disease Parameters

- a) A "measurable" serum M-protein is ≥ 1 g/dL or a "measurable" urine M-spike is ≥ 200 mg/24 hours or "measurable light chains" are either a serum kappa or lambda FREE light chain of ≥ 10 mg/dL along with an abnormal kappa to lambda free light chain ratio, patient is considered to have "measurable" disease.
- b) The serum free light chain (FLC) assay is of particular use in monitoring response to therapy in patients who have light-chain disease. When using this assay, it is important to note that the FLC levels vary considerably with changes in renal function and do not solely represent monoclonal elevations. Thus both the level of the involved and the uninvolved FLC isotype (i.e., the involved/uninvolved ratio or involved-uninvolved difference) should be considered in assessing response. The serum FLC assay should be used in assessing response if the baseline level of the involved FLC is ≥ 10 mg/dL and abnormal kappa/lambda ratio (when primary determinant of response).
- c) For patients with initial baseline 24-hr UPEP samples demonstrating ≥ 100 mg/24 hrs, patients with continue to have 24-hr UPEP samples day 1 of each cycle. Once 24-hr UPEP is <100 mg/24 hrs, patient can have random UPEP with IFE until achieving negativity. If initial baseline 24-hr UPEP sample is IFE positive and/or <100 mg/24, patients can have random UPEP samples with IFE until achieving negativity. Once random UPEP and IFE is negative, no further urine samples are needed (unless primary determinant of response)
- d) In order to be classified as a response, confirmation of serum monoclonal protein, serum immunoglobulin free light chain (when primary determinant of response) and urine monoclonal protein (when primary determinant of response) results must be made by verification on two consecutive determinations at different timepoints.
- e) Compression fracture does not exclude continued response and may not indicate progression; findings of worsening compression fracture will be subject to interpretation of the clinical investigator.

Minimal Residual Disease

For patients undergoing MRD or end of study assessment, the first pulled bone marrow sample will be sent for multi-parametric flow cytometry as a priority. Flow cytometry based assay to rule out MRD (defined as less than 20 abnormal plasma cells) in bone marrow aspirates of CR/sCR patients. For patients with samples demonstrating between 10-20 abnormal plasma cells, cases will be reviewed with hematopathologist and clinical investigator on a case by case basis to determine whether sample is considered MRD positive. Patients with <CR/sCR are considered MRD positive. We will use the MSKCC flow cytometry MRD method which is based on 10-colors in a single tube.¹⁶ The test demonstrates highly similar results when compared to the current Euroflow approach. This test is validated and already in clinical use at MSK. Immunophenotyping of aberrant plasma cells by flow cytometry currently involves, but is not limited to, the use of the following reagents: CD138, CD19, CD45, CD38, and CD56. Characteristic changes in immunophenotypically abnormal plasma cells (CD38 bright and/or CD138 positive) include but are not limited to decreased or absent CD19 and CD45, decreased CD38, increased CD56, decreased CD27, decreased CD81, increased CD117. For patients with non-evaluable samples at MRD assessment, patients can opt for repeat MRD assessment or continue to receive a total of 12 cycles of CRd. For those patients that are MRD negative by flow cytometry during their routine pre-stem cell collection bone marrow assessments,

the result will count towards their MRD evaluation.

Traditional Response Criteria from International Myeloma Working Group Criteria for Multiple Myeloma²²

Evaluation of Response Criteria

- a) Stringent Complete Response (sCR)
 - o Complete Response as defined below plus: Normal FLC ratio and absence of clonal cells in bone marrow by immunohistochemistry or immunofluorescence (presence/absence of clonal cells is based on the kappa/ lambda ratio).
- b) Complete Response (CR)
 - o Negative immunofixation on the serum and urine and disappearance of any soft tissue plasmacytomas and <= 5% plasma cells in bone marrow
- c) Very Good Partial Response (VGPR)
 - o Serum and urine M-protein detectable by immunofixation but not on electrophoresis or 90% or greater reduction in serum M-protein plus urine M- protein level <100mg per 24h. If the serum and urine M-protein are unmeasurable, a \geq 90% decrease in the difference between involved and uninvolved FLC levels is required in place of the M- protein criteria.
- d) Partial Response (PR)
 - o \geq 50% reduction in M protein and reduction in 24-h urinary M-protein by \geq 90% or to < 200 mg per 24h . If the serum and urine M-protein are unmeasurable, a \geq 90% difference between involved and uninvolved FLC levels is required in place of the M- protein criteria
- e) Stable Disease (SD)
 - o Not meeting criteria for CR, VGPR, PR or progressive disease. All categories also require no known evidence of progressive or new bone lesions if radiographic studies were performed. Radiographic studies are not required to satisfy these response requirements.
- f) Progressive disease (PD)
 - o Requires any one or more of the following:
 - Increase of \geq 25% of nadir in:
 - Serum M-component and/or (absolute increase must be \geq 0.5 g/dl. The serum M-component increases of \geq 1gm/dl are sufficient to define relapse if starting M-component is \geq 5 gm/dl.
 - Urine M-component and/or (the absolute increase must be \geq 200 mg/24h
 - Only in patients without measureable serum and urine M-protein levels: the difference between involved and uninvolved FLC levels. The absolute increase must be >10 mg/dl.
 - Bone marrow plasma cell percentage: the absolute % must be \geq 10%
 - Definite development of new bone lesions or soft tissue plasmacytomas or definite increase in size of existing bone lesions or soft tissue plasmacytomas
 - Development of that can be attributed solely to the plasma cell proliferative disorder

g) Relapse from CR

- Any one or more of the following:
 - Reappearance of serum or urine M-protein by immunofixation or electrophoresis. (Appearance of monoclonal or oligoclonal bands that are different from original isotype may not be defined as "relapse from CR". Often times, such bands may indicate fluctuations in immunological parameters that are not reflective of MM disease. In these situations, immunofixation and electrophoresis will be interpreted by the clinician before being labeled as "relapse"^{23,24}.)
 - Development of $\geq 5\%$ plasma cells in the bone marrow
 - Appearance of any other sign of progression (ie, new plasmacytoma, lytic bone lesion, hypercalcemia)

Progression-Free Survival

PFS is defined as time of start of treatment to time of progression or death, whichever occurs first.

Overall Survival

Overall survival is defined as the time of start of treatment to death from any cause.

Toxicity Criteria

The following adverse event management guidelines are intended to ensure the safety of each patient while on the study. The descriptions and grading scales found in the revised NCI Common Terminology Criteria for Adverse Events (CTCAE) version 4.0 will be utilized for AE reporting. All appropriate treatment areas should have access to a copy of the CTCAE version 4.0. A copy of the CTCAE version 4.0 can be downloaded from the CTEP web site

(http://ctep.cancer.gov/protocolDevelopment/electronic_applications/ctc.htm#ctc_40).

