In the past decade, multiple myeloma patients have reached deeper response rates with use of effective anti-myeloma therapeutics, immunomodulatory agents and proteasome inhibitors, approximating up to 75% patients achieving near-complete response (>90% decrease in monoclonal protein) or complete response (100% decrease in monoclonal protein){Kumar, 2008 #716}. In general, improved therapeutics and deeper response rates have resulted in improved overall survival of multiple myeloma patients across most age groups. As a result, there has been an increasing demand for the development of sensitive assays to detect minimal residual disease (MRD) in treated MM patients. In MM patients receiving autologous stem cell transplant, MRD-negative status using multi-parametric flow cytometry (MFC) is associated with improved progression free survival and overall survival. Similar studies using next generation sequencing methods for MRD have also been shown to be associated with improved outcomes in MM MRD-negative patients. In our prior study, among the 25 patients with CR/sCR that were assessed by MFC for immunophenotypic abnormal plasma cells; 25 out of 25 were negative for (MRD with an overall MRD negative rate of 25/43 (58%) (*2 patients did not have evaluable samples) using MFC. Using next generation sequencing molecular tests, the CR/sCR MRD negative rate was 13/33 (39%) (*12 patients did not have evaluable samples) (Sequenta platform). In patients with NDMM treated with CRd, 12-month progression-free survival for MRD-negative vs MRD-positive status by flow cytometry and next-generation sequencing was 100% vs 79% (95% CI, 47%-94%; $P < .001$) and 100% vs 95% (95% CI, 75%-99%; $P = .02$), respectively.

Minimal Residual Disease Platforms

A recent survey including 30 major institutions in the US found major heterogeneity in MRD testing of multiple myeloma by flow cytometry¹⁶. In brief, there was considerable variation in the number of bone marrow cells analyzed (events) and number of abnormal plasma cells needed to define the presence of MRD, which affects maximum possible sensitivity. The maximum detection sensitivity ranged from 0.0005% to 0.02%, a 100-fold difference in sensitivity. Also, the variation in antibodies studied and definition of an abnormal plasma cell by flow cytometry affected the ability to differentiate normal from neoplastic plasma cells.

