4.2 Intervention

- Cycle 1 ONLY: Carfilzomib 20 mg/m² per dose, days 1 and 2; Carfilzomib 45 or 56 mg/m² per dose, days 8, 9, 15, and 16
- Cycles 2- up to 12: Carfilzomib 45 or 56 mg/m² per dose, days 1, 2, 8, 9, 15, and 16
- Cycles 1- up to 12: Lenalidomide 25 mg/day, days 1–21 every 28 days
- Cycles 1-4: Dexamethasone 20 mg/dose, days 1, 2, 8, 9, 15, 16, 22, and 23
- Cycles 5- up to 12: Dexamethasone 10 mg/dose, days 1, 2, 8, 9, 15, 16, 22 and 23
- After receiving first 4 cycles, patients who are considered to be eligible for subsequent high dose therapy/autologous stem cell transplant (ASCT) will undergo autologous stem cell harvesting for potential use in the future. For patients who choose to undergo stem cell harvest, the next cycle may be delayed for up to 7 weeks.
- Patients will receive maximum up to 12 cycles of induction combination therapy of CRd. Total number of cycles delivered will be determined by response status.
 - Patients achieving ≤PR after completion of 4 cycles of therapy will stop protocol therapy.
 - For patients achieving >PR at end of 4 cycles, patients will continue to receive combination therapy with maximum up to 12 cycles.
 - Patients obtaining CR/sCR at any point in serum and urine will undergo MRD testing using multi-parametric flow cytometry.
 - Patients who attain minimal residual disease (MRD) negative status by flow cytometry will stop treatment after 2 additional cycles (maximum 12 cycles).
 - Patients who are MRD positive by flow cytometry will stop treatment at completion of 12 cycles. Patients converting from MRD positive status to negative status on subsequent MRD testing can stop after 2 additional cycles
 - Patients achieving <CR/sCR (and >PR at end of 4 cycles) will stop treatment at completion of 12 cycles.

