- h. Bone marrow aspirate and biopsy can be performed +/- 21 days of intended cycle day or achievement of CR/sCR. The first pull bone marrow aspirate will be sent for MRD testing for Multiparametric flow cytometry. Bone marrow aspirate and biopsy will be sent to evaluate for histopathology, flow cytometry (bone marrow immunophenotyping of plasma cells), heavy/light chain immunoglobulin rearrangement. Aspirate lysate will also be sent for cell sorting into CD 138- and + fractions and whole bone marrow lysate for HOTB storage so molecular profiling with GEP and DNA-based sequencing at baseline can be performed as correlative work. For patients, reaching CR/sCR MRD negative timepoint earlier where MRD negative status is confirmed at earlier bone marrow evaluation, bone marrow aspiration and biopsy at end of study will be optional. Otherwise, all other bone marrow biopsies are mandatory.
- i. After study therapy ends, follow-up will be 1 month after study end date. Patients may be followed at more frequent time intervals, and thereafter if clinically indicated. Patients who have progressive disease while on therapy will be followed with restaging scans and laboratory tests as clinically indicated. At disease progression, marrow and FDG-PET/CT are optional but recommended.
- j. For patients with initial baseline 24-hr UPEP samples demonstrating ≥ 100 mg/24 hrs, patients will continue to have 24-hr UPEP samples day 1 of each cycle. Once 24-hr UPEP is < 100 mg/24 hrs, patient can have random UPEP with IFE until achieving negativity. If initial baseline 24-hr UPEP sample is IFE positive and/or < 100 mg/24, patients can have random UPEP samples with IFE until achieving negativity. Once random UPEP and IFE is negative, no further urine samples are needed (unless patient's disease is primarily measurable by 24 hr urines)

- k. FDG-PET scan will be performed on patients at baseline, end of therapy or upon suspicion of progressive disease as clinically indicated. End of therapy FDG-PET scan can be performed +/- 21 days.
- l. Treatment window for day 1 of start of each cycle is +/- 7 days. Treatment window for intra-cycle carfilzomib doses is + 2 days. .

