The phase II component of this trial will explore the efficacy of the combination therapy using the carfilzomib dose selected in the phase I trial. The primary endpoint is CR/sCR MRD negativity (MRD-) rate by flow cytometry upon or prior to completion of 12 cycles of therapy. Patients with <CR/sCR are considered MRD positive. Based on previous research an CR/sCR MRD- rate by flow cytometry of 45% would be promising enough to warrant further investigation, while a rate of 20% would not be promising for further investigation. Using a Simon's optimal two-stage design, the first stage of the trial will enroll 14 patients. This includes the three-six patients treated at the MTD in the phase I trial. If three patients or fewer are CR/sCR MRD- by flow cytometry, the trial will stop due to a lack of efficacy; otherwise, an additional 11 will enroll to a total sample size of 25 at end of phase II. If at least eight patients are MRD- (at the MTD), the intervention will be considered promising for further research. The type I error is set at 0.10 and the type II error is set at 0.10. If the true MRD-rate is 20%, the probability of early termination is 70%. For patients that come off trial prior to completion of 4 cycles of therapy, due to reasons unrelated to disease progression or toxicities, patients can be replaced (max 3) for MRD evaluation as part of the phase II assessment.

It is anticipated that 1-2 patients per month may enroll on this trial; thus, approximately one year is anticipated as the accrual period for the phase II study. The total maximum possible projected sample size for the study is 37 patients.

Secondary endpoints for both Phase I and II:

1. To estimate the overall response rate (ORR) according to International Myeloma Working Group criteria at each cycle and as the best response during the treatment of up to 12 cycles. In addition to ORR, the rates of VGPR+CR and CR alone will also be estimated and reported. The exact 95% confidence intervals will also be included.
2. Kaplan-Meier methodology will be used to estimate progression-free survival and overall survival. Estimates of survival along be with 95% confidence intervals will be provided for select time points.

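### The phase II primary endpoint leaves samples with 10-20 abnormal plasma cells to case-by-case review without criteria

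*Combined protocol and SAP*

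**What the plan says.** Section 14.0 makes the phase II primary endpoint the "CR/sCR MRD negativity (MRD-) rate by flow cytometry upon or prior to completion of 12 cycles of therapy". Patients below CR/sCR count as MRD positive, so only CR/sCR patients can be borderline.

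Section 12.0 (Minimal Residual Disease) gives the cell-count rule: "Flow cytometry based assay to rule out MRD (defined as less than 20 abnormal plasma cells"), applied to marrow aspirates of CR/sCR patients. The parenthesis is loosely placed, but the only sensible meaning is that fewer than 20 cells rules MRD out. The next sentence takes samples with 10-20 cells and says that "cases will be reviewed with hematopathologist and clinical investigator on a case by case basis to determine whether sample is considered MRD positive". Section 10.0 refers back to institutional practice and Section 12.0 and adds no count rule.

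The decision rules are in Section 14.0. At 14 patients, "If three patients or fewer are CR/sCR MRD- by flow cytometry, the trial will stop due to a lack of efficacy"; at 25, eight or more negatives is a promising result. The reference rates are 20% and 45%.

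MRD status also drives treatment length. Section 4.2 says: "Patients who attain minimal residual disease (MRD) negative status by flow cytometry will stop treatment after 2 additional cycles".

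**The concern.** A sample with 10-19 cells meets the rule-out cut and also falls in the review band. A sample with exactly 20 fails the cut but is still reviewable. No criteria, tie-break or masking is stated, and one of the two reviewers is the clinical investigator of a single-arm study. Section 14.0 does not say whether the numeric result or the reviewed call enters the counts at 14 and 25, nor which of them the 20% and 45% rates assume.

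The protocol knows that the cut matters. In describing variation between institutions, Section 3.1 names the number of cells analysed and the "number of abnormal plasma cells needed to define the presence of MRD, which affects maximum possible sensitivity". With so few patients, one call can decide a look, and two careful readers of Section 12.0 could count the same patient differently.

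**Working it through.** **Inputs (Section 14.0).** n1 = 14, stop at 3 or fewer; n = 25, promising at 8 or more; p0 = 0.20, p1 = 0.45; both error rates set at 0.10. From Section 3.1: in the prior study 25 of 43 patients (58%) were flow-negative, including 25 of 25 in CR/sCR.

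**Step 1: the plan's own figures.** P(promising | p) = Σ over x = 4 to 14 of P[Bin(14, p) = x] × P[Bin(11, p) ≥ 8 − x].
- Early stopping at p = 0.20: P[Bin(14, 0.20) ≤ 3] = 0.698 (stated 70%).
- Type I error at 0.20: 0.0933.
- Power at 0.45: 0.9026.

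The design reproduces; the issue is what is counted, not the design.

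**Step 2: direction.** Against the cut of fewer than 20, review can only turn a negative into a positive. The exception is a count of exactly 20.

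**Step 3: power if negatives are removed.** One patient in 25 is 4 percentage points. The shifts are assumed, because no frequency is given for the band.

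| Rate with all 10-19 negative | None removed | 1 in 25 removed | 2 in 25 removed |
|---|---|---|---|
| 45% | 0.903 | 0.824 (at 41%) | 0.709 (at 37%) |
| 58% | 0.993 | 0.982 (at 54%) | 0.959 (at 50%) |

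The first row is a loss only if the 45% was set with every 10-19-cell sample counted negative. These losses are also upper bounds. A patient called positive may be negative on later testing, and unless MRD negativity was confirmed earlier, the end-of-study marrow is required (Section 10.0, footnote h: "Otherwise, all other bone marrow biopsies are mandatory").

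**Step 4: how common could positive calls be?** With 0 positives among 25 CR/sCR patients, the one-sided 95% upper limit is 1 − 0.05^(1/25) = 11.3%. Removing 1 in 25 from 45% is 4/45 = 8.9% of negatives, inside that limit; removing 2 in 25 is 8/45 = 17.8%, outside it. This is only a guide, because the centre and assay differ.

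**Step 5: one reclassified negative.** Take one randomly chosen negative and call it positive. A promising verdict is lost in two ways:
- the total was exactly 8; or
- the total t exceeded 8, stage 1 had exactly 4 negatives, and the chosen patient was one of those four (probability 4/t).

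| True rate | Total exactly 8 | Stage 1 exactly 4, t > 8, weighted 4/t | Sum |
|---|---|---|---|
| 20% | 0.050 | 0.004 | 5.4% |
| 45% | 0.056 | 0.025 | 8.1% |
| 58% | 0.0044 | 0.0064 | 1.1% |

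Each applies only if that patient is in the 10-20 band.

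**Separate minor item (Section 12.0, response criteria).** For patients without measurable M-protein, VGPR needs at least a 90% decrease in the involved-uninvolved light-chain difference. PR also has a 90% threshold, but as a difference between the two chains, with no mention of a decrease. Read as a decrease, anyone meeting PR already meets VGPR, so PR is empty. Read literally, it does not measure change. Section 6.1 admits patients measurable only by light chains. Each patient misscored moves ORR by 1/37 = 2.7 to 1/25 = 4.0 percentage points; the number affected is not given.

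**The case against.** The strongest reply is that Section 12.0 states a general rule followed by an exception. Review exists to decide whether a sample is positive, so 10-19 is negative by default and only exactly 20 is unclear. That stands. A reader might infer two rival rules with no default, but the order and purpose of the sentences do not support it. A three-zone reading (below 10 negative, 10-20 reviewed, above 20 positive) is also possible, though not stated. On any of these readings the review has no criteria.

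Second, the impact may be negligible. The only evidence in the documents on positive flow calls among CR/sCR patients is 0 of 25, and at that study's 58% rate power stays at 0.959 or above even with two patients lost. This also stands, and it limits the size of the point.

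Third, a fixed count is not a fixed sensitivity, because Section 12.0 gives no minimum number of events, and a fixed cut removes expert judgement. That is fair. The fix makes the count reproducible; it does not standardise sensitivity.

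On the light-chain item, the wording looks like a drafting slip, since Sections 12.0 and 14.0 both point to International Myeloma Working Group criteria. It still needs correcting, but it adds no weight to the main point.

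**Conclusion.** The point holds as an unspecified adjudication rule in the primary endpoint; it should be fixed. That the criteria are missing is certain. The size of the effect is not, because the documents give no frequency for 10-20-cell samples. Power falls from 0.903 to 0.824 or 0.709 for 1 or 2 patients in 25 only if the 45% rate counted all such samples negative; if it already reflects reviewed calls, the loss is nil.

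A reader might infer that discretion inflates the chance of a false promising result. The documents do not support this. Against the stated cut, review removes negatives except at exactly 20, and type I error would rise only if the 20% rate had been set on a stricter cut, which is nowhere stated. A reader might also put the chance that one call changes the verdict at 17-18% for true rates of 20% and 45%. That total includes changes from positive to negative that the cut rules out, and it treats every promising result with exactly 4 of 14 as lost. The supported figures are 5.4%, 8.1% and 1.1%.

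The light-chain item affects ORR only. Read as a decrease, the wording understates ORR; read literally, the direction is unknown. VGPR-or-better, CR and the four-cycle rule are unaffected, since PR and SD fall on the same side of that rule.

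**What to change.** In Sections 12.0 and 14.0, classify every CR/sCR sample for the primary analysis at both looks by the one stated cut: fewer than 20 abnormal plasma cells negative, 20 or more positive. Do this without knowledge of the running count. Add two sensitivity analyses: one with all 10-20-cell samples counted positive, and one using the reviewed calls.

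State whether the endpoint call is the same call that sets treatment length, and reconcile Sections 1.0, 4.2 and 12.0 accordingly. No treatment rule is proposed here.

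Separately, for ORR scoring only, restate light-chain PR as a decrease in the involved-uninvolved difference. Set its threshold below that for VGPR, consistent with the 50% M-protein criterion in the same item.

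The cost is wording and two short analyses, with no new visit or sample. The downside is that experts cannot override a borderline sample in the primary count.
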